- c) Aggressive end-of-life care (any of the following three criteria: chemotherapy within 14 days before death, hospitalization within 30 days before death, or admission to hospice 3 days or less before death), among high-risk patients who die

Aim 2: Conduct a quantitative evaluation using secondary data (obtained via EMR and census, for patients, and by survey, for clinicians) to identify moderators of implementation effects on SIC documentation. [Note: the clinician survey will be conducted within a separate study funded by this grant and has been submitted for IRB approval as a separate protocol; data across the studies will be linked by clinician name and study ID.]

1. Primary objective:

Evaluate for heterogeneity of implementation effects on SIC documentation by race/ethnicity, income, and geographic location as well as by clinician and inner setting factors.

Aim 3: Perform a mixed methods qualitative/quantitative analysis of secondary patient-reported data from the SIC priming questionnaire, among patients randomized to the patient nudge arm.

BACKGROUND AND RATIONALE:

Serious illness conversations (SICs) that elicit patients' values, goals, and care preferences, particularly early in the disease trajectory, are an evidence-based practice, improve patient mood and

quality of life,⁷⁻¹² and are recommended by national guidelines.¹³⁻¹⁵ However, most patients with advanced cancer die without a documented SIC and there are well-documented health disparities in implementation for racial and ethnic minorities.¹⁶⁻²¹ Clinician barriers to initiating SICs include optimism bias, or the belief that one's own patient is unlikely to experience a negative event; uncertainty about prognosis and appropriate timing; and fear that bringing up end-of-life issues may be distressing to patients.^{26,27} Patient barriers to SIC initiation include fear of discussing the end of life and beliefs that SICs are not appropriate until late in the course of cancer.¹⁵ While previous studies have tested financial incentives for SIC documentation, little research has evaluated behavioral economics-informed strategies to align *both* clinicians and patients towards earlier SICs.

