Usual practice. Usual practice will consist of targeted text messages identifying patients at high risk of mortality based on a validated machine learning prognostic algorithm, as well as clinician-directed performance feedback (WITHOUT peer comparison), thereby serving as an active control arm.

We will use RCA to optimize implementation strategies to ensure face validity and maximum effect. We will focus on optimizing content, messaging, and design. RCA procedures will involve design meetings with study team, discussions with administrators and clinicians who are members of our Implementation Lab, as well as piloting of nudges with clinicians and patients to elicit feedback.

2. Data Collection:

The electronic medical record and other Penn Medicine secondary databases will be used to collect information on practices, clinicians, and patients. These systems collect this information as part of routine clinical care. We will also collect data from the U.S. Census via publicly available datasets.

Aim 1

The primary outcome is SIC documentation among high-risk patients. This will be measured at the patient level as a binary outcome, ascertained over the 6-month period following the index outpatient clinical encounter. The electronic medical record has an Advanced Care Planning (ACP) section in which ACP notes are documented. Any note documented in this section will be classified as an ACP, and only the subset of notes that include a preformatted SIC template will be classified as a SIC.

The secondary outcomes will each be measured at the patient level as a binary outcome, ascertained over the 6-month period following the index outpatient clinical encounter:

- SIC documentation, among all patients
- Palliative care referral, among high-risk patients
- Aggressive end-of-life care (any of the following three criteria: chemotherapy within 14 days before death, hospitalization within 30 days before death, or admission to hospice 3 days or less before death), among high-risk patients who die

Aim 2

Aim 2 measures, collected through the electronic medical record and using publically available U.S. Census data, will include:

- *Patient-level data*: age, sex, race/ethnicity, cancer type, cancer stage, health insurance (e.g., Medicare, Medicaid, commercial);
- *Clinician-level data*: years in practice and patient panel size;
- *Practice-level data*: setting (community vs. hospital-based), urban vs. non-urban location, and health insurance mix;

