- *Ecologic-level data* linked at the patient- and practice-level, including median income and educational attainment.

Aim 3

Aim 3 data collection will additionally consist of patient-reported content obtained during the course of the study in response to the SIC priming questionnaire, among 1,166 participants randomized to the patient nudge study arm who completed the SIC priming questionnaire (Appendix 2).

3. Genetic Testing:

Not applicable

4. Use of Deception:

Not applicable

5. Statistical Analysis:

Aim 1

The primary outcome will be modeled in a time-to-event analysis using a Cox proportional hazards model, with cluster-correlated robust standard errors to account for clustering by clinical site. SIC documentation, as defined above, will serve as the primary event outcome. Days between the index clinical encounter (at which the nudge exposure period begins) and SIC documentation will serve as the time variable. The design is a 2x2 factorial, which breaks down into 4 study arms (defined by clinician cluster and patient randomization at the index clinical encounter): nudge to clinician only, nudge to patient only, nudge to both, or usual practice. Cox regression will estimate hazard ratios for the main effects (Aim 1) and a ratio of hazard ratios for the interaction term (Aim 2). Significance will be determined using the z-score corresponding to each of the estimated effects, using a two sided type 1 error of 5%. All enrolled patients will be included in the intention-to-treat analysis, and subjects will be censored at the time of last follow-up or death, should they

not have been observed to have a documented SIC during the follow-up period. Covariates will be assessed across study arms and included in the Cox model if unbalanced across arms.

We will use our fitted Cox model to generate predicted probabilities of SIC documentation within 6 months, via marginal standardization, as well as median time to documented SIC across arms. The functional form of the model will be checked using cumulative martingale residuals, and the proportional hazards assumption will be checked using scaled Schoenfeld residuals.

The secondary outcomes will be similarly modeled. All hypothesis tests will use a two-sided alpha of 0.05 as the threshold for statistical significance.

Aim 2

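### Aggressive end-of-life care is a known yes/no for every decedent, but its only analysis instruction points to a Cox model that would censor the known non-events at death

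*Combined protocol and SAP*

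**What the plan says.** The secondary objectives under Aim 1 and the Data Collection section (Study Procedures, section 2, Aim 1) define aggressive end-of-life care as any of three criteria: "chemotherapy within 14 days before death, hospitalization within 30 days before death, or admission to hospice 3 days or less before death". The population is high-risk patients who die. Data Collection also says that every secondary outcome is binary at patient level and ascertained over the 6 months after the index encounter.

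The Statistical Analysis section (Study Procedures, section 5, Aim 1) sets out a Cox model for the primary outcome:

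- Time variable: "Days between the index clinical encounter (at which the nudge exposure period begins) and SIC documentation will serve as the time variable".
- Censoring: "subjects will be censored at the time of last follow-up or death, should they"; the rest of that sentence limits the rule to patients without a recorded SIC.
- Prediction: "We will use our fitted Cox model to generate predicted probabilities of SIC documentation within 6 months".

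The secondary outcomes then receive one instruction on modelling: "The secondary outcomes will be similarly modeled". Nothing else in the document gives aggressive end-of-life care an event date, a time variable, a censoring rule or a model.

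**The concern.** A Cox model suits an outcome that may or may not have happened by the time observation stops. Here everyone in the analysis set has died, so the answer is complete at death. If a decedent without aggressive care is censored at death, a known no is treated as an unknown.

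Three things follow:

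- The effect measure is a ratio of hazards from the index encounter. The objective asks how often decedents received aggressive care.
- The information in the known non-events is lost, and more is lost the commoner aggressive care is.
- The analyst must choose the event date (first qualifying care, last qualifying care or death). Two analysts could follow the text and report different quantities, and the choice could be made after the data are seen.

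**Working it through.** **No figure to reproduce.** The plan gives no rate, death count or power for this outcome. From the documents: 5,500 high-risk patients, 66 clinician clusters (Power and Sample Size), two-sided alpha 0.05. Assumed: 6-month mortality 35% (range 20-50%); aggressive-care rate p of 30%, 50% or 70%; the same death timing in all arms; 1:1 allocation on each factor. This gives 5,500 × 0.35 = 1,925 decedents, or 962.5 per level of each factor.

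**Step 1. Patient nudge, precision.** Let d be the number with aggressive care in a group.

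- Cox, non-events censored at death: var(log HR) ≈ 1/d1 + 1/d0.
- Yes/no analysis: var(log RR) ≈ (1−p1)/d1 + (1−p0)/d0.
- With equal p, the ratio of standard errors is 1/√(1−p).

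| p | SE ratio | 1,925 decedents carry the information of |
|---|---|---|
| 30% | 1/√0.70 = 1.20 | 1,925 × 0.70 ≈ 1,350 |
| 50% | 1/√0.50 = 1.41 | 1,925 × 0.50 ≈ 960 |
| 70% | 1/√0.30 = 1.83 | 1,925 × 0.30 ≈ 580 |

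Simulation with 66 clusters of 83 patients gave about 1.20, 1.42 and 1.85.

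**Step 2. Patient nudge, power for an assumed 43% versus 50%.**

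- d1 = 962.5 × 0.43 = 413.9; d0 = 962.5 × 0.50 = 481.3; |ln 0.86| = 0.1508.
- Cox: variance 1/413.9 + 1/481.3 = 0.00449, SE 0.0670, z = 2.25, power Φ(2.25 − 1.96) = 61%.
- Yes/no: variance 0.57/413.9 + 0.50/481.3 = 0.00242, SE 0.0492, z = 3.07, power Φ(3.07 − 1.96) = 87%.

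Simulations with clustering gave about 55-70% against 84-88%. Over 20-50% mortality the simulated ranges were 34-81% and 59-95%.

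**Step 3. Clinician nudge, precision.** Clinician clusters are randomised, so variation between them adds the same term to both variances. If the log odds of aggressive care vary with SD s, the log risk varies with SD of about s(1−p). With 33 clusters per group the added term is 2[s(1−p)]²/33.

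- At p = 50%, s = 0.3: 2 × 0.15²/33 = 0.00136. Cox: 2/481.3 + 0.00136 = 0.00552. Yes/no: 2 × 0.5/481.3 + 0.00136 = 0.00344. SE ratio √(0.00552/0.00344) = 1.27.
- Simulated ratios at 30/50/70% were about 1.13/1.28/1.60 for s = 0.3 and 1.07/1.15/1.32 for s = 0.6. The formula gives 1.13/1.27/1.58 and 1.06/1.13/1.31.

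**Step 4. Windows that open before the index encounter.** With a constant death hazard and 35% mortality by day 180, the hazard is −ln(0.65)/180 = 0.00239 per day. The chance of death within 30 days is 1 − exp(−30 × 0.00239) = 6.9%, and 6.9/35 is about 20% of decedents. Over the assumed death-timing patterns this share runs from 1% to 49%. For these patients the 30-day hospitalization window starts before time zero.

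**Step 5. Only if the prediction step is also carried over.** With events dated at death, the cumulative hazard by day 180 is about p × (ln 1,925 + 0.577) = 8.14p. At p = 50% the predicted probability is 1 − exp(−4.07) = 98%. Dating events up to 30 days before death gave about 84-85% by simulation.

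**The case against.** **The outcome is labelled binary, so a binary model is intended.** This is the best defence, and the label does fit a yes/no analysis. It does not settle the matter, because the same section also calls the primary outcome binary and the plan analyses that by Cox. It is also true that the instruction might carry over only the arms, model terms and robust standard errors. That reading is possible but nowhere stated.

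**The 6-month ascertainment window answers the question about care before the index encounter.** In part. It suggests that only later care counts, but it does not say what happens to a look-back window that starts earlier.

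**Cox gives nearly the same ratio and a valid test.** With equal death timing this stands. A reader might go further and infer bias: if deaths came earlier in one arm, the hazard ratio would mix timing of death with care received. The documents give no reason to expect the nudges to shift death timing, so that stronger claim is not made.

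**The precision loss does not apply equally to both nudges.** This stands. A reader might apply 1.20/1.41/1.83 to the clinician nudge too, but step 3 shows a smaller loss there once clusters vary.

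**The inflated predicted probabilities are hypothetical.** This stands. The prediction sentence names SIC documentation only, and no sentence asks for that output for this outcome.

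**The simulations cluster on the clinician unit, while Statistical Analysis names clinical site.** Also correct. The figures are not operating characteristics of site-level clustering. The level of clustering is a separate issue.

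**Conclusion.** The point holds as a specification fault in one secondary outcome that should be fixed. The natural reading of the plan puts a fully observed yes/no outcome into a Cox model, censors known non-events at death and leaves the event date open. The result would not estimate the proportion of decedents who received aggressive care.

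The size is a loss of precision: for the patient nudge, power of about 55-70% instead of 84-88% in the 43% versus 50% example, and a smaller loss for the clinician nudge when clusters differ. These figures rest on assumed mortality, care rates, equal death timing and clustering on the clinician unit. The textual gap depends on none of them.

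The documents do not support reading this as a biased comparison, as a certain overstatement of the proportion, or as a problem for the primary analysis.

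**What to change.** Limit the cross-reference to the other two secondary outcomes, SIC documentation among all patients and palliative care referral. For this outcome add:

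> Aggressive end-of-life care will be analysed as yes/no among high-risk patients who die within 6 months of the index encounter, by modified Poisson regression with the same factorial terms and cluster-robust standard errors at the level used for the primary outcome, reporting risk ratios, with risk differences by marginal standardization. Only qualifying care on or after the index encounter counts; a sensitivity analysis counts the full look-back window.

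The main analysis needs no new data and the code is simpler; the sensitivity analysis needs care records from up to 30 days before the index encounter. The primary analysis does not change. There are two downsides. The effect is a risk ratio rather than a hazard ratio, so it is not on the same scale as the other outcomes. Conditioning on death after randomisation remains a limitation under either model and should be stated when the result is reported.

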Rationale for clinician nudge using mortality prediction and peer comparison. Due to optimism bias, clinicians routinely overestimate the life expectancy of patients with advanced cancer^{28,29} and delay SICs until too late in the disease course. In part because of this, clinicians reinforce a social norm that early SICs are not part of routine oncology care. Providing an objective assessment of predicted mortality risk may help counteract optimism bias among clinicians, and help them identify patients most likely to benefit from SICs. Moreover, that individuals desire to conform to an approved behavior (an injunctive norm) and the behavior of others (a descriptive norm) may contribute to low observed SIC rates, and may also afford an opportunity for intervention. We expect that periodically reminding clinicians of their own performance on SIC documentation, while providing both an injunctive norm (citing national and institutional guidelines) and a descriptive social norm (displaying the behavior of their best performing peers), will lead clinicians to conform more closely to these norms, as has been shown in studies conducted in other contexts.^{23,30,31}

Rationale for patient nudge using priming. Priming is a type of nudge that frames information to activate one's self-efficacy and willingness to engage in behavior change.³² This type of nudge has not previously been evaluated as a tool to promote SICs for patients with cancer. We will test the added impact of a patient nudge designed to prime patients and, in turn, their clinicians to having a SIC.

CHARACTERISTICS OF THE STUDY POPULATION:

1. Target Population and Accrual:

The target population includes approximately 5,500 high-risk patients with cancer cared for by approximately 166 medical and gynecologic oncology clinicians at the following hospital and free-standing community practice sites of the Penn Medicine Abramson Cancer Center (ACC), referred to hereafter as the "Implementation Laboratory": Hospital of the University of Pennsylvania (HUP), Pennsylvania Hospital (PAH), Penn Presbyterian Medical Center (PPMC), Chester County Hospital (CCH), Valley Forge Medical Center, Radnor Medical Center, Cherry Hill Medical Center, Voorhees Medical Center, Sewell Medical Center and Regional Hematology Oncology Associates. The trial will be conducted pragmatically, and patients will accrue as they are seen in follow-up at a participating practice site by an eligible provider.

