We will evaluate for heterogeneity of implementation effects on SIC documentation by including an interaction term between study arm and, separately, patient factors, such as race/ethnicity, income, and geographic location; clinician factors; and inner setting factors. Evidence for effect modification will be judged based on the z-score corresponding to the ratio of hazard ratios (interaction term) using again a two-sided alpha of 0.05 as the threshold for statistical significance.

Aim 3

We will perform a mixed methods qualitative/quantitative analysis of 1,166 participant responses to the SIC priming questionnaire, using de-identified data obtained during the course of the pragmatic clinical trial.

In preparation for conducting a qualitative analysis of participant responses, a thematic codebook will be developed inductively. At least two coders will independently review de-identified participant responses to question 2 of the SIC priming questionnaire, and meet regularly to discuss common themes, to resolve discrepant coding, and to establish inter-rater reliability. When necessary, the Principal Investigators will serve as a third independent coder to resolve discrepancies. Kappa statistics will be generated to estimate inter-rater reliability. The iterative coding process will continue until all coding is complete with a Kappa score greater than or equal to 0.80. NVivo qualitative software will be used for codebook generation, data management, and to pull qualitative data points as needed for analysis.

Participant responses to the SIC priming questionnaire will be described quantitatively (questions 1 and 3) or qualitatively (question 2). For the latter, representative quotes will be selected to illustrate the key themes that emerge from qualitative coding. We will evaluate for associations between participant responses and patient, clinician and inner setting factors.

Power and Sample Size

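### Aim 2 tests practice-level moderators, which vary over only ten sites, with a site-clustered z-score and no few-cluster correction, so the false-positive rate is roughly 10 to 19% rather than 5%

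*Combined protocol and SAP*

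**What the plan says.** - **Test.** Under Statistical Analysis, Aim 2, heterogeneity is assessed by "including an interaction term between study arm and, separately, patient factors, such as race/ethnicity, income, and geographic location; clinician factors; and inner setting factors". The decision rule is "Evidence for effect modification will be judged based on the z-score corresponding to the ratio of hazard ratios (interaction term". The threshold is two-sided 0.05, as in Aim 1. One rule covers every moderator.
- **Variance estimator.** The Aim 2 text does not restate it. The Aim 1 text specifies a Cox model with robust standard errors clustered on clinical site, refers each estimate to a z-score, and says the Cox regression also supplies the Aim 2 interaction. No t reference or few-cluster adjustment appears in either place.
- **Practice-level moderators.** Data Collection, Aim 2 lists "setting (community vs. hospital-based), urban vs. non-urban location, and health insurance mix", and ecologic data "linked at the patient- and practice-level, including median income and educational attainment".
- **Number of sites.** Target Population and Accrual describes "hospital and free-standing community practice sites of the Penn Medicine Abramson Cancer Center" and names five ("Hospital of the University of Pennsylvania (HUP), Pennsylvania Hospital (PAH), Penn Presbyterian Medical Center (PPMC), Chester County Hospital (CCH), Valley Forge Medical Center") and five more ("Radnor Medical Center, Cherry Hill Medical Center, Voorhees Medical Center, Sewell Medical Center and Regional Hematology Oncology Associates").
- **Standing.** Inner setting factors are part of Aim 2's primary objective.

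**The concern.** A moderator that is constant within a site carries at most ten values, however many patients are enrolled. The evidence on it is a comparison of ten site-specific nudge effects, with 10 − 2 = 8 residual degrees of freedom. The planned z-score uses a sandwich variance built from those same ten clusters. That variance is biased low when clusters are few, and its own sampling error is ignored when the ratio is referred to a normal distribution. Both faults push toward rejection.

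At stake is whether a significant interaction with, say, community versus hospital setting can be read at its stated 5% error rate. Several such variables are to be tested, each at the same threshold.

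**Working it through.** **1. Inputs from the documents.** Ten sites (5 + 5); 66 physician-APP units; 5,500 high-risk patients; z reference; two-sided 0.05. The plan's 83 patients per unit reproduces: 5,500 / 66 = 83.3. The power table covers the two nudges and their interaction with each other. It gives no figure for moderator tests, and no baseline event rate from which to rebuild it. The figure to check here is therefore the nominal 5%.

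**2. Assumptions not in the documents.** Each listed site is one practice. Setting splits them 4 versus 6. Site sizes, event rate and between-site variation are as given in step 5.

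**3. Reference distribution alone.** If the standard error were unbiased with 8 df, P(|t₈| > 1.96) = 8.6%. The correct critical value is 2.306.

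**4. Adding the sandwich bias (idealised: ten equally informative sites).** Let each site effect have variance σ².
- True variance of the difference between the two group means: σ²(1/4 + 1/6) = 0.417σ².
- An uncorrected sandwich divides squared residuals by n rather than n − 1, so its expectation is σ²[(3/4)/4 + (5/6)/6] = σ²(0.1875 + 0.1389) = 0.326σ².
- Ratio 0.326 / 0.417 = 0.783; on the SE scale, √0.783 = 0.885.
- The 1.96 cut-off then acts like 1.96 × 0.885 = 1.73, and P(|t₈| > 1.73) is about 12%.

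No variation in nudge effect between sites is needed for this.

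**5. Simulation, no true moderation, 4 versus 6 sites, 66 units of 83 patients.**
- *Run A:* 2,000 trials per case; exponential regression standing in for Cox; 15% control SIC rate; 35% six-month mortality; between-unit SD of log hazard 0.5; equal or skewed sites.
- *Run B:* 600 trials per case; Cox model; within-unit correlation 0.1; 10% or 30% baseline SIC rate; site SD of log baseline hazard 0.3; equal or uneven sites. Monte Carlo SE is √(0.14 × 0.86 / 600) = 1.4 points at 14%.

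Both let the site SD of the nudge log HR run from 0 to 0.3.

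| Test of nudge × setting | Run A | Run B |
|---|---|---|
| Site-clustered z (the plan) | 12–17% | patient 11–19%, clinician 12–19% |
| Same, site SD = 0 | within 12–17% | 12–16% |
| Site-clustered SE with G/(G−1) and t₈ | not run | 6–12% |
| Unit-clustered z, site SD = 0, patient nudge | 5–7% | 5–7% |
| Unit-clustered z, site SD = 0.2, patient nudge | 12–15% | 13–29% |
| Site-level t on 8 df | 3–5% | 2–6% (patient nudge only) |

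For the clinician nudge, unit-clustered z gave 6 to 8% at SD 0 in run B. At SD 0.2 it gave about 10% in run A and 8 to 12% in run B.

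Two further simulations put the planned test at 10–16% and 11–16%. The first of them put the site-level t-test at 4–7%.

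**6. Other Aim 2 moderators under the same site-clustered z.** A patient-level moderator with no effect was rejected in 10–11% of trials, and a clinician-level one in 12–14%.

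**The case against.** **Clustering is already handled.** A reader might infer that the interaction is judged by a patient-level z-score that treats patients as independent. The documents do not support that: the Aim 1 text specifies site clustering and links the same regression to Aim 2. The much larger rates for a model-based z (26 to 45% for the patient nudge at a site SD of 0.3, and 36 to 63% for the clinician nudge) therefore do not describe this plan. What remains is the few-cluster fault.

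**The fault is not peculiar to practice-level variables.** This stands. Step 6 shows it in the other Aim 2 tests, so moving only the practice-level moderators would leave the rest at about twice nominal. In the same runs the Aim 1 main effects, which share the estimator, were rejected in 9–12% of trials; the present point is confined to Aim 2.

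**If inference is to these ten named sites, a real difference between groups of sites is not a false positive.** This is fair for the scenarios in which effects vary by site. It does not touch the 12–16% found when they are identical everywhere.

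**Scope.** Income and geographic location appear in the plan as patient factors, and ecologic data are linked at patient level too. Those versions vary within a site. Clinician survey data come from a separate protocol. Only variables constant within a site need site-level inference.

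**Consequence.** A reader might infer that moderator findings will steer roll-out. No such use or decision rule appears in the documents.

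**Conclusion.** The point holds for the planned site-clustered z-score. For a moderator constant within a site, the test rejects a true null in roughly 10 to 19% of trials, about two to four times the stated 5%. The direction does not depend on nudge effects differing between sites; the reference distribution alone accounts for 8.6%. The exact size depends on the assumed 4-versus-6 split, site sizes, event rate and heterogeneity, none of which the documents give.

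Changing the cluster variable to the physician-APP unit is not enough for these moderators. It gives about 5 to 8% when nudge effects do not vary by site, but about 15% for the patient nudge at a site SD of 0.2 in the log HR, and up to 29% in run B. This is an interpretive fault in part of Aim 2's primary objective, and it should be corrected.

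**What to change.** In Statistical Analysis, Aim 2:

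1. State the variance estimator and cluster variable explicitly.
2. Remove moderators that are constant within a site from the z-score rule. Estimate the nudge log HR in each site, compare these across the moderator with a t reference on (number of contributing sites − 2) df, and report the results as exploratory. Say how a site with units in only one clinician arm is handled, since it yields no clinician-nudge estimate of its own. The site-level calculation in run B covered the patient nudge only.
3. For patient- and clinician-level moderators, cluster on the randomised physician-APP unit (66 clusters) or apply a small-sample correction. G/(G−1) with t₈ left 6–12% in the practice-level case, so that simple form should not be relied on at ten clusters. No rejection rate is available here for unit clustering with these moderators, so a short simulation before the SAP is fixed would be worthwhile.

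The cost is SAP wording and a small second-stage analysis. The downside is that practice-level moderators will rarely reach significance, which reflects what ten sites can support.
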